6.1.5 Equipment

Calibrated thermometer for each subject. Maintenance will constitute in the form of thermometer replacement if required. Calibration is not necessary for the duration of the study

6.2 Investigational Device(s) and Comparator(s)

The comparator used is the subject's own product use which is assessed at W0.

6.3 Participants

6.3.1 Recruitment

A dedicated email address and phone number will be assigned to the study.

Subjects will be recruited through several channels:

1. The Clinical Research Platform will inform its network of GP's in Dublin and surrounding areas of the study. GP's will inform relevant patients and give them the Subject Information Leaflet/Invitation to participate

CE-GAX001-01 V4.0

CR: 144

- 2. HS specialist dermatologists in Dublin and surrounding areas will be notified of the study and can inform patients.
- 3. An invitation will be shared with a closed patient support group online.

Candidates can call or email to express interest in the study. Candidates will be screened based on the inclusion/exclusion criteria below.

6.3.2 Inclusion Criteria

In order to be eligible to participate in this study, an individual must meet all of the following criteria:

- 1. Provision of signed and dated informed consent form in English
- 2. Stated willingness and ability to comply with all study procedures (in English) and availability for the duration of the study
- 3. Female, aged >18
- 4. Diagnosed with Hidradenitis Suppurativa
- 5. Hidradenitis Suppurativa affecting the axilla
- 6. Exuding lesion that requires wound dressings

6.3.3 Exclusion Criteria

An individual who meets any of the following criteria will be excluded from participation in this study:

- 1. Recent surgery <3 months in axilla
- 2. Psoriasis, Dermatitis or skin conditions/rash other than Hidradenitis Suppurativa on or near affected area
- 3. Pregnancy or lactation
- 4. Known allergic reactions to components of Hidrawear AX

6.3.4 Criteria for Withdrawal or Discontinuation

Subjects may withdraw from the study at any time without any rationale and without compromising their future medical care.

The subject may also be removed from the study by their physician or the consultant if they feel it is the best interest of the subject.

The use of the Hidrawear garment will be suspended if the patient presents with pyrexia and/or infection.

6.3.5 Enrolment

Subjects will be enrolled on Day 0

CE-GAX001-01

V4.0

CR: 144

Subjects with Hidradenitis Suppurativa of the axilla are candidates for enrolment into this pilot study. Following review of the inclusion and exclusion criteria, eligible subjects will be invited to participate in the study.

A Subject information leaflet will be provided to each subject in the study. Information non the study, the fact that it involves research, the purpose of the study, the potential risks/benefits will be given to all subject.

All subjects will sign an informed consent form before they can be enrolled into the study and begin proceedings

The subject's participation is completely voluntary, and they can withdraw from the study at any time throughout. Their withdrawal will have no impact on any services / treatment they are currently receiving or the relationship with their doctor.

6.3.6 Replacement of Subjects

Drop-out rates of up to 6 subjects (25%) are anticipated.

A cohort of 23 subjects will be selected from pre-screened applicants.

Applicants not selected will have the option to join a waiting list in the instance of a drop out or excluded subject.

Applicants on the waiting list will be contacted and invited to consent and enrol into the study subject to approval from the PI.

Subjects will be replaced by recommencing the enrolment process as detailed in 6.3.4.

6.3.7 Duration of the Clinical Investigation

Planning, CIP and essential documents – 3 months

6 weeks expected recruitment and 22 days subject participation.

Data analysis and Reporting – 3 months

6.3.8 Expected Study Duration for Participants

From the time of enrolment, subjects with participate for 22 days: 2 days on site or home visit, 20 days in the home setting.

6.3.9 Number of Subjects

23 subjects

6.3.10 Time to Select all Subjects

The recruitment period will remain open until 23 subjects are enrolled. Estimated time required is 6 weeks.

Page 23 of 56

CE-GAX001-01

V4.0

CR: 144

6.4 Procedures

6.4.1 Pilot Study Procedures

Procedures & Assessments	Day 0	Day	Day	Day	Day	Day	V2;
	Enrolment	1 - 6	7	8 - 13	14	15 - 20	End of
	Assessment						Intervention
							Day 21
Informed Consent	X						
Medical / HS History	X						
Armpit Clinical assessment	X						X
Inclusion/exclusion criteria	Х						
Observe Subject using usual method of dressing wound	Х						
Dermatology Quality or life index survey, Ease of Use, Comfort, Time, Pain scale.	Х		Х		Х		Х
Subject trained on use of HidraWear Ax	Х						
Subject trained on use of Thermometer	Х						
Subject daily use of Hidrawear AX		Х	Х	Х	Х	Х	X
Temperature Record	Х	Х	Х	Х	Х	Х	Х
Observe Subject using Hidrawear AX							X
Daily Survey		Х	Х	Х	Х	Х	Х
Checkup phone call			Х		Х		
Researcher Data Entry	Х	Х	Х	Х	Х	Х	Х
Adverse Events	Х	Х	Х	Х	Х	Х	Х

CE-GAX001-01

V4.0

CR: 144

6.4.2 Factors with Potential to Compromise the Outcome/Interpretation of the Results

Subjects are living with a debilitating disease and are often affected in more than one anatomical location.

This study is capturing/measuring quality of life based on an improved method and product indicated for use in dressing an axillary wound only. While an improvement in ease of use, comfort, time, secure dressing retention may be captured, an improvement in quality of life scores may be compromised due to other affected areas impacting negatively on the subject's daily life.

6.4.3 Follow-up Medical Care

Subjects will remain under the care of their GP throughout the study.

CE-GAX001-01

V4.0

CR: 144

7 STATISTICAL CONSIDERATIONS

7.1 Statistical Design

This pilot study is a small-scale preliminary investigation to evaluate feasibility, time, cost, adverse events and improve upon the study design prior to performance of a full-scale investigation. The data collected will provide the estimates needed of the potential treatment effect and the likely variability in the response at baseline and over time.

7.2 Sample Size

A sample size of 23 subjects, chosen based on feasibility, will be investigated. The sample corresponds to an estimated margin error of 0.18 in the primary response.

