	Study Duration: 9 months - from when the study opens to enrolment until completion of data analyses			
	Subject participation duration: 3 weeks			
Sample size and study	Sample size: 23			
duration:	Female, over 18, presenting with HS of the axilla			
	Study Duration: 9 months - from when the study opens to enrolment until completion of data analyses			
	Subject participation duration: 3 weeks			

CR: 144

	In order to be eligible to participate in this study, an individual must meet all of the following criteria:				
	3				
	1. Provision of signed and dated informed consent form in English.				
	2. Stated willingness to comply with all study procedures and availability for the duration of the study				
	3. Female, aged >18				
	4. Diagnosed with Hidradenitis Suppurativa				
	5. Hidradenitis Suppurativa affecting the axilla				
	6. Exuding lesion that requires wound dressings				
	Exclusion Criteria:				
	1. Recent surgery <3 months in axilla				
1	2. Psoriasis, Dermatitis or skin conditions/rash other than Hidradenitis Suppurativa on or near affected area				
	3. Pregnancy or lactation				
	4. Known allergic reactions to components of Hidrawear AX				
Primary Performance					
Endneinter	Primary outcome measure:				
	Subjects own product use (Day 0) vs Hidramed (Day 21)				
	• Ease of Use Day 21 vs Day 0				
Secondary	Secondary outcome measures:				
Performance	 Ease of Use Day 21 vs Day 0 Comfort, measured 				
Endpoints:	on a 5-point scale Day 21 vs Day 0				
	 Visual Pain Analogue Scale Day 21 vs Day 0 				
	Time Day 21 vs Day 0				
	 Additional equipment used – mirror, scissors etc 				
	Could dressing be applied without raising arms over head				
	Necessity to stretch/contort body to apply dressing				
	Did subject need assistance				
	9 months - from when the study opens to enrolment until completion of data analyses.				
	Subject participation: 22 days, Visit day 0, and day 21.				

CE-GAX001-01

V4.0

CR: 144

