6.1.3 Primary and Secondary Endpoints

Primary Endpoint

• The change in the ease of use at week 3 compared to Day 0

Secondary Endpoints - Subject Assessment

- Ease of use W2 vs W1
- Comfort measured on a 10 point scale D21 vs D0
- Pain measured on a 10 point scale D21 vs D0
- Time measured on a 10 point scale D21 vs D0
- Dressing retention confidence measured on a 10 point scale D21 vs D0

Secondary Endpoints – Nurse Assessment

- Necessity to stretch/contort the body to apply dressing
- Did subject need assistance
- Could dressing be applied without raising arms over head
- Additional equipment used- mirror, scissors etc.

Outcome selection rationale:

- Assessment of ease of use as primary outcome was selected as most users have voiced frustration
- Comfort was selected as we wish to learn if Hidrawear AX is comfortable to use.
- Dressing retention confidence was selected as user have voiced frustration
- Dressing related pain was selected as HidraWear AX may reduce unnecessary patient distress due to dressing/adhesive related pain
- Time was selected as regular wound dressing changes are time consuming (6)

CE-GAX001-01

V4.0

CR: 144

DLQI was selected as it a validated tool that has been commonly used for assessment of quality of life for HS subjects. will assess if Hidrawear AX is better than the current products used by HS subjects.

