6.1.4 Methodology

Before the study commences on site, a survey will be shared into select closed patient groups online, to capture the patient experience of living with Hidradenitis Suppurativa (HS) in terms of self-managing wound care and the impact that HS wound care has on patients' day to day life, physically, financially and emotionally.

A secure and confidential survey tool (Typeform) will be used. This is governed under EU data legislation and encrypted to ensure privacy. The survey will not collect any identifying information and is a precursor to the HidraWear AX Pilot Study.

Day 0

Subjects will visit trial site or have a home visit from research nurse.

Following consent and enrolment, Subjects will be asked to demonstrate or explain their usual method of dressing their wound using their usual wound dressing products.

Subjects will assess this activity based on ease of use, comfort, experienced pain, confidence in dressing retention and time, using a 10 point visual analogue scale. (see appendix 2)

The subjects will complete a Dermatology Quality of Life Index Survey. (see appendix 5)

The research nurse will assess the activity based on whether the subject needs assistance, uses additional equipment, contorts or stretches their body, can dress the wound without raising their arms above their head. (See appendix 4)

Day 1-21

Daily Check in with Subjects:

Each day, at 1pm, subjects will receive an email requesting them to check in with the researcher by answering 3 questions.

- 1. What is your temperature?
- 2. How many dressings did you use in the last 24 hours?
- 3. Any comments?

This check in should take less than 5 minutes to complete.

Subjects will be required to respond by 5pm each evening. If subject has not responded by 5pm, a reminder text message will be sent to them.

If subject does not respond within 24 hours, the research nurse will call the subject to check in and take answers over the phone.

CE-GAX001-01

V4.0

CR: 144

Weekly Check in with Subjects:

On day 7 and 14 subjects will be asked to complete the Dermatology Quality of life survey and questions on Ease of use, comfort, pain and confidence, at home. A link to the surveys will be emailed to them at 1pm in the afternoon with their daily check in.

Subjects will be required to respond by 5pm each evening. If subject has not responded by 5pm, a reminder text message will be sent to them.

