7.3 Level of Significance and Power of the Clinical Investigation

This is a post-market clinical follow-up. The size of the study was not determined based on a power calculation.

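### Does the unexplained 0.18 margin of error in section 7.2 call for a correction to the plan?

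*Combined protocol and SAP*

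**What the plan says.** Protocol section 7.2 has two sentences. The first gives the size and its basis: "A sample size of 23 subjects, chosen based on feasibility, will be investigated". The second attaches a precision figure: "The sample corresponds to an estimated margin error of 0.18 in the primary response".

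The surrounding text bears on how to read that figure:

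- Section 6.1.3 defines the primary endpoint as "The change in the ease of use at week 3 compared to Day 0". It defines no responder or other binary version.
- Section 6.1.4 has subjects rate "ease of use, comfort, experienced pain, confidence in dressing retention and time, using a 10 point visual analogue scale".
- The Clinical Investigation Summary has the phrase "on a 5-point scale Day 21 vs Day 0" in a line that runs ease of use and comfort together.
- Section 7.1 says the pilot will supply the "estimates needed of the potential treatment effect and the likely variability in the response at baseline and over time".
- Section 7.3, despite its heading, gives no significance level and states: "The size of the study was not determined based on a power calculation".
- Section 7.5 has no statistical stopping rule.

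**The concern.** A margin of error can be interpreted only if the reader knows what is being estimated, in what unit, at what confidence level, and with what assumed SD or proportion. Section 7.2 gives none of these. Because there is no power calculation, 0.18 is also the only numerical statement of precision in the plan.

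The natural reading is scale points on the 10-point ease-of-use rating. On that reading 0.18 is a very tight interval for 23 subjects, and it implies an SD of change that no section supports. Section 7.1 in fact treats the variability as unknown. If the figure were badly wrong, a reader might expect far more precision from this pilot than it can give, and might carry that expectation into the full-scale investigation that section 7.1 has in view.

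**Working it through.** **Inputs from the documents.** n = 23 (7.2); margin 0.18 (7.2); endpoint is the within-subject change, Day 21 against Day 0 (Summary, 6.1.3); 10-point scale (6.1.4). Confidence level, SD and proportion are not given, so each route below needs an assumption.

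**Can 0.18 be reproduced?** Not from the stated inputs alone. Three readings were tried.

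*1. Mean change, in scale points.* Half-width = t(0.975, n−1) × SD / √n.

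- At n = 23 with the t quantile: 2.074 / 4.796 = 0.432 SD. With the normal quantile: 1.96 / 4.796 = 0.409 SD.
- SD of change needed for 0.18 points at 95%: 0.18 / 0.4324 = 0.416 (t) or 0.18 / 0.4087 = 0.440 (normal).
- At 90%: 0.18 / 0.3580 = 0.503 (t) or 0.18 / 0.3430 = 0.525 (normal).
- The required SD in points is the same whether the scale has 10 points or 5.
- For assumed SDs of change of 1, 2 and 3 points, the 95% half-width would be 0.43, 0.86 and 1.30 points.

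*2. Mean change, in SD units.* 0.18 × √23 = 0.863, which corresponds to about 60% two-sided confidence. A 95% half-width of 0.18 SD would need 121 subjects.

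*3. A proportion.* Half-width = z × √(p(1−p)/n).

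| Assumption at n = 23 | Half-width |
|---|---|
| 95%, p = 0.5, Wald | 1.96 × √(0.25/23) = 0.204 |
| 95%, maximum, Wilson | 0.189 |
| 95%, p = 0.75, Wald | 1.96 × √(0.1875/23) = 0.177 |
| 90%, p = 0.5, normal quantile | 0.171 |
| 90%, p = 0.5, t quantile | 0.179 |

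Solving the 95% Wald formula for exactly 0.18 gives p(1−p) = 23 × (0.18/1.96)² = 0.194, so p = 0.263 or 0.737. Any p from about 0.71 to 0.76, or its mirror image, rounds to 0.18.

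**What this shows.** Readings 1 and 3 can each give 0.18 under an assumption the plan does not state. Reading 2 can do so only at an unusual confidence level. A proportion near 0.75 is an ordinary planning value and rounds to the printed figure, but section 6.1.3 defines no proportion. The figure therefore cannot be derived, and it cannot be refuted. Setting 0.18 against 0.43 SD shows no contradiction, because the unit of 0.18 is unknown.

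**Where is 0.18 used?** The sample size rests on feasibility (7.2) and not on power (7.3). There is no statistical stopping rule (7.5). The hypothesis in 5.2 and the performance claims in 5.3 contain no margin. No later section refers to 0.18.

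**The case for a change.** The strongest case for a change is that the sponsor chose to print a precision figure, that it stands alone, and that most readers would take it as scale points. If the SD of change were 1 to 3 points (an assumed range), the 95% half-width would be 0.43 to 1.30 points. That is 0.432/0.18 = 2.4 to 1.297/0.18 = 7.2 times the printed value. Correcting one sentence would cost no subjects and no visits.

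The omission is real, and a clarifying line would do no harm. The rest carries less weight:

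- The comparison holds only on the scale-points reading, which the documents do not establish.
- The obvious replacement, a half-width of 0.43 SD with the SD unknown, is true of any mean from 23 subjects. It says nothing about precision in points, and it chooses a mean change where the plan names no analysis method.
- The link to a full-scale study is weak. Section 7.1 takes the effect and variability estimates from the collected data, and those do not depend on 0.18.

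Two side issues do not alter this. With 17 completers the 95% half-width would be 2.120 / 4.123 = 0.514 SD, but that requires all 6 anticipated drop-outs (7.4) to go unreplaced, and section 6.3.6 plans otherwise: "Subjects will be replaced by recommencing the enrolment process as detailed in 6.3.4". Section 5.1 says 20 subjects where sections 6.3.9 and 7.2 say 23. That is a clerical mismatch and does not touch the use of 0.18.

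**Conclusion.** No change to the plan is needed. Section 7.2 leaves out the basis of its margin of error, and the documents do not allow it to be rebuilt for the ease-of-use change. The figure is not shown to be wrong: it fits a mean change with an SD of about 0.42 to 0.44 points at 95%, or a proportion near 0.75 (half-width 0.177). Neither assumption is stated.

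The size of the consequence is nil for the sample size, the data collected, the analysis and the conclusions. An analyst will report the observed change with its SD and confidence interval, which makes the planning figure redundant.

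This rests on two points. The documents show that feasibility alone set the 23 subjects and that nothing downstream uses 0.18. It is assumed that the report will state precision from the observed data and will not repeat 0.18 as the precision achieved.

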7.3 Level of Significance and Power of the Clinical Investigation

This is a post-market clinical follow-up. The size of the study was not determined based on a power calculation.

7.4 Expected Drop-out Rates

Drop-out rates of up to 6 subjects (25%) are anticipated.

7.5 Criteria for Stopping Clinical Investigation

There are no stopping rules on statistical grounds

CE-GAX001-01

V4.0

CR: 144

8 DATA MANAGEMENT

8.1 Procedures for Data Review, Database Cleaning, and Issuing/Resolving Queries

All data will be collected on paper.

Surveys at The Hermitage Clinic will be completed on paper by subjects and transcribed in to Typeform by research nurse

Typeform account will be held by the sponsor and access will be available only to the research nurse and sponsor.

Data will be sent electronically for data analysis to [name] at NUIG through secure intranet server.

Subject personal information will be encrypted, accessible only by the study nurse with the use of an inscription key for the duration of the study. This will mean that subject information will be identifiable by only by a subject number, rather than personal information.

All investigation data will be stored electronically for a period of 7 years following study completion on a password protected file.

Data analysis shall be conducted by [name], NUI Galway.

8.2 Other Aspects of Clinical Quality Assurance

The study will be performed in accordance with this protocol, regulations (21 Code of Federal ICH guidelines for Good Clinical Practice (GCP), the regulations on electronic records and electronic signature (21 CFR 11), and the most recent guidelines of the Declaration of Helsinki (Section 19.2).

The study will also be performed in accordance with any laws and regulations in force in the country in which the research is carried out.

Participants should be informed that they may withdraw from the study at any time. They will receive all information that is required by local regulations and ICH guidelines. The principal investigator or a designated representative will provide the sponsor or its representative with a copy of the IRB/IEC-approved ICF before the start of the study. This Study will be conducted according to ICH GCP and strict adherence to the protocol.

Monitoring visit will be conducted by external organization which will provide quality assurance during the study.

Monitoring will include personal visits and telephone communication to assure that the investigation is conducted according to the protocol, standard operating procedures, GCP guidelines, and applicable regulatory requirements. Quality control procedures will be applied to each stage of data handling to ensure that all data are reliable and have been processed correctly.

By signing this protocol, the investigator grants permission to personnel from the sponsor, its representatives, and appropriate regulatory authorities, for on-site monitoring of all appropriate study documentation, as well as on-site review of the procedures employed in eCRF generation, where clinically appropriate

CE-GAX001-01

V4.0

CR: 144

9 AMENDMENTS TO THE CLINICAL INVESTIGATION PLAN

The Clinical Investigation Plan may require an amendment during the conduct of a clinical investigation. Any amendment to the clinical investigation plan will be agreed between the Sponsor and the Principal Investigator. The amendments will be notified to, or approved by, the Ethics Committee as appropriate.

CE-GAX001-01

V4.0

CR: 144

10 CLINICAL INVESTIGATION PLAN COMPLIANCE

The study will be carried out in accordance with ISO 14155.

The protocol, informed consent form(s), recruitment materials, and all subject materials will be submitted to the Research Ethics Committee (REC) for review and approval. Approval of both the protocol and the consent form must be obtained before any subject is enrolled. Any amendment to the protocol will require review and approval by the REC before the changes are implemented to the study. In addition, all changes to the consent form will be REC-approved; a determination will be made regarding whether a new consent needs to be obtained from subjects who provided consent, using a previously approved consent form.

The Principal Investigator will assure that no deviation from, or changes to the protocol will take place without prior agreement from the sponsor, funding agency and documented approval from the REC except where necessary to eliminate an immediate hazard(s) to the trial subjects. All personnel involved in the conduct of this study have completed ICH GCP and relevant training.

CE-GAX001-01

V4.0

CR: 144

11

